14.2.1. Delegation of Responsibility

When specific tasks are delegated by an investigator, including but not limited to conducting the informed consent process, the Principal Investigator is responsible for providing appropriate training, are competent to perform the tasks they have been delegated and adequate supervision of those to whom tasks are delegated. Where there is a sub investigator at a site, the sub investigator should not be delegated the primary supervisory responsibility for the site. The investigator is accountable for regulatory violations resulting from failure to adequately supervise the conduct of the clinical study.

14.3. Institutional Review Board/ Ethics Committee

The investigational site will obtain the written and dated approval/favorable opinion of the IRB/EC for the clinical investigation before recruiting subjects.

A copy of the written IRB/EC and/or competent authority (CA) approval of the protocol (or permission to conduct the study) and ICF, must be received by the sponsor before recruitment of subjects into the. Prior approval must also be obtained for other materials related to subject recruitment or which will be provided to the subject.

Any amendment to the protocol will require review and approval by the IRB/EC before the changes are implemented to the study. All changes to the ICF will be IRB/EC approved; a determination will be made regarding whether a new ICF needs to be obtained from participants who provided consent, using a previously approved ICF. Annual IRB/EC approval and renewals will be obtained throughout the duration of the study as required by applicable local/country laws or regulations or IRB/EC requirements. Copies of the study reports and the IRB/EC continuance of approval must be provided to the sponsor.

14.4. Sponsor Responsibilities

All information and data sent to BSC concerning subjects or their participation in this study will be considered confidential by BSC and will be kept confidential in accordance with all applicable laws and regulations. Only authorized BSC personnel and/or a BSC representative including, but not limited to Contract Research Organization (CRO), will have access to this information. Authorized regulatory personnel have the right to inspect and copy all records pertinent to this study. Study data collected during this study may be used by BSC for the purposes of this study, publication, and to support future research and/or other business purposes, such as overseeing and improving the performance of its device, new medical research and proposals for developing new medical products and procedures. All data used in the analysis and reporting of this study or shared with a third-party researcher will be without identifiable reference to specific subjects.

Information received during the study will not be used to market to subjects; subject names will not be placed on any mailing lists or sold to anyone for marketing purposes.

14.4.1. Role of Boston Scientific Representatives

BSC personnel may perform certain activities to ensure study quality. These activities may include the following.

- Observing testing or medical procedures to provide information relevant to protocol compliance
- Reviewing collected data and study documentation for completeness and accuracy

Boston Scientific personnel will not do the following.

- Practice medicine
- Provide medical diagnosis or treatment to subjects

- Discuss a subject's condition or treatment with a subject
- Independently collect critical study data (defined as primary or secondary endpoint data)
- Enter data in electronic data capture systems or on paper case report forms

14.5. Insurance

Where required by applicable regulation in China, BSC will provide insurance coverage for subjects in the study. If any study related health injury occurs, claims and compensation will be made, where required, and BSC will assume the responsibility per insurance procedure, except in the case that damages are incurred due to deviation of the protocol, intentional or serious negligence at the site.

15. Monitoring

Monitoring will be performed during the study to assess continued compliance with the protocol and applicable regulations. In addition, the clinical research monitor verifies that study records are adequately maintained, that data are reported in a satisfactory manner with respect to timeliness, adequacy, and accuracy, and that the Principal Investigator continues to have sufficient staff and facilities to conduct the study safely and effectively. The source documents include but not limit to signed ICF, medical records, image (if any), lab tests (if any) and SAEs. The Device deficiencies, relationships of AE and medical device/ procedure recorded in the CRF will be considered as source documents in this study. The sponsor will put a plan in place to document the specific monitoring requirements.

The Principal Investigator/institution guarantees direct access to original source documents by BSC personnel, their designees, and appropriate regulatory authorities. If the source document can't be acquired for subjects who went to non-investigation hospital or examined by non-investigator, the certified copies should be got and maintained. Source document related to SAE should be copied (if applicable) and sent to BSC safety, as specified in chapter 17.

The study may also be subject to a quality assurance audit by BSC or its designees, as well as inspection by appropriate regulatory authorities. It is important that the Principal Investigator and relevant study personnel are available during on-site monitoring visits or audits and that sufficient time is devoted to the process.

16. Potential Risks and Benefits

16.1. *Anticipated Adverse Events and Anticipated Adverse Device Effects of SpaceOAR system*

All subjects were treated with SpaceOAR system, which were implanted between prostate and anterior rectum before participation in this study. It slowly absorbs via hydrolysis and is cleared from the implant site in approximately six months. Anticipated adverse events and Anticipated Adverse Device Effects of SpaceOAR system are specified as below:

- Pain associated with SpaceOAR hydrogel injection
- Pain or discomfort associated with SpaceOAR hydrogel
- Local inflammatory reactions
- Infection
- Urinary retention
- Mucosal damage, ulcers
- Bleeding
- Constipation
- Urgency (e.g., urinary and rectal)
- Allergic reaction
- Embolism
- Fistula
- Penetration
- Syncope

16.2. Risks associated with Participation in the Clinical Study

This study is an observational study, that the medical data generated in the clinical practice will be used, no new or additional intervention will be imposed on the subjects, no foreseen additional risks. But the risks of PCa and treatment may not be reduced when subjects take part in this study. During the data collection in the study, no private information that can identify the subject will be collected, such as, name, ID number, hospital number, telephone number, address etc.

16.3. Risk Minimization Actions

Additional risks may exist. Risks can be minimized through compliance with this protocol, performing procedures in the appropriate hospital environment, adherence to subject selection criteria, close monitoring of the subject's physiologic status during follow-ups and by promptly supplying BSC with all pertinent information required by this protocol.

16.4. Anticipated Benefits

There are no guaranteed benefits from participation in this study. However, information gained from this study may be of benefit to others with the same medical conditions.

17. Safety Reporting

17.1. Reportable Events by investigational site to Boston Scientific

It is the responsibility of the investigator to assess and report to BSC any event which occurs in any of following categories:

- All adverse events
- All serious adverse events
- All Adverse Events related to Study Device
- All Serious Adverse Events related to Study Device
- All Adverse Events related to RT
- All Serious Adverse Events related to RT
- Unanticipated Adverse Device Effects/Unanticipated Serious Adverse Device Effects
- All Device Deficiencies
- New findings/updates in relation to already reported events

When possible, the medical diagnosis should be reported as the Event Term instead of individual symptoms.

If it is unclear whether an event fits one of the above categories, or if the event cannot be isolated from the device or procedure, it should be submitted as an adverse event and/or device deficiency.

Any reportable event, experienced by the study subject after informed consent, whether prior to, during or after RT, must be recorded in the eCRF.

Underlying diseases and chronic conditions are not reported as AEs unless there is an increase in severity or frequency during the investigation. Death should not be recorded as an AE, but should only be reflected as an outcome of one (1) specific SAE (see Table 17-1 for AE definitions).

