Study design	
This study protocol is for the second part of SpaceOAR real world study in which long term follow-up visits will be performed (up to 1 year) outside Boao Medical Tourism Pilot Zone. The SpaceOAR real world study is a retrospective and prospective, single arm, observational study (Protocol of SpaceOAR RWS Windchill#: 92743236). Subjects with localized T1-T2 prostate cancer who have already been injected with the SpaceOAR and have received radiotherapy or will receive radiotherapy will be enrolled, and clinical data related to radiotherapy will be collected.
 
For subjects who have already completed radiotherapy before study kick-off, clinical data will be collected retrospectively, such as data related to radiotherapy, AE (if any) and MRI (if any). Follow up visit will be completed if applicable.
 
For subjects who receive therapy after study kick-off, follow up visits at 2 weeks, 6 weeks, 3 months and 10 months after radiotherapy will be scheduled to assess bowel, urinary and sexual function and quality of life.

An observational study to evaluate the safety and effectiveness of radiotherapy for localized T1-T2 prostate cancer in China after injection of SpaceOAR Hydrogel

An observational study of radiotherapy after injection of SpaceOAR Hydrogel

Space OAR observational Study Design

Planned Number of Subjects	Up to 20 eligible subjects will be enrolled to generate data including 14 subjects at least.
Planned Number of Sites / Countries	1 site, Shanxi Provincial Cancer Hospital

An observational study to evaluate the safety and effectiveness of radiotherapy for localized T1-T2 prostate cancer in China after injection of SpaceOAR Hydrogel

An observational study of radiotherapy after injection of SpaceOAR Hydrogel

Primary Endpoint	
Reduction of dose volume of rectum receiving x Gy as specified below, which is measured from CT simulation scans acquired pre and post SpaceOAR hydrogel injection, that is Vx Gy :
 
• For conventionally fractionated regimen: V70Gy• For moderately hypofractionated regimen: V46Gy, V37Gy• For ultrahypofractionated regimen: V29 Gy, V18. 1 Gy, V36 Gy 
Dose to the anterior rectum is quantified by computing a rectal dose-volume histogram (DVH).

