3 months post RT: the questionaries of EPIC and EQ-5D-5L will be completed to assess the functions of urinary, rectum and health related Quality of life; Adverse event and Device Deficiency will be collected, if applicable.

10 months post RT: MRI will be performed; Adverse event and Device Deficiency will be collected, if applicable.

NOTE: For subjects who have received RT (after SpaceOAR injection), applicable follow up will be performed after participation in this study to assess adverse event and device deficiency, if any, then to collect clinical data. The clinical data before participation will be collected retrospectively at same time.

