10.2. General Statistical Methods

10.2.1. Analysis Sets

The effectiveness set, and safety set include all subjects who have radiotherapy after injection of SpaceOAR hydrogel.

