17.4. Investigator Reporting Requirements

The communication requirements for reporting to BSC are as shown in Table 17-3.

Note: For data collected retrospectively, there is no specific reporting requirements for retrospective study in current laws and regulations. In view of feasibility of operation and specialty of retrospective study, Communication timeline is specified as below.

Table 17-3: Investigator Reporting Requirements

Event Classification	Communication Method	Communication Timeline post-market studies* (EU MDR 2017/745, MDCG 2020-10/MEDDEV 2.12/1: GUIDELINES ON A MEDICAL DEVICE VIGILANCE SYSTEM)
Unanticipated Adverse Device Effect / Unanticipated Serious Adverse Device Effect	Complete AE eCRF page with all available new and updated information.	
 For data collected prospectively: within 24 hours of first becoming aware of the event. For data collected retrospectively, within 5 business day of the event identified or collected during data collection Terminating at the end of the study.
	Provide all relevant source documentation (de-identified/ pseudonymized) for reported event.	
 Upon request of sponsor.
Serious Adverse Event including serious adverse effects	Complete AE eCRF page with all available new and updated information.	
 For data collected prospectively: within 24 hours of first becoming aware of the event. For data collected retrospectively, within 5 business day of the event identified or collected during data collection Reporting required through the end of study
	Provide all relevant source documentation (de-identified/ pseudonymized) for reported event.	
 Upon request of sponsor
Device Deficiencies (including but not limited to malfunctions, use errors, and inadequacy in information supplied by the manufacturer, including labelling) Note: Any Device Deficiency that might have led to a	Complete eCRF page with all available new and updated information.	
 For data collected prospectively: within 24 hours of first becoming aware of the event. For data collected retrospectively, within 5 business day of the event identified or collected during data collection Reporting required through the end of the study

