Event Classification	Communication Method	Communication Timeline post-market studies* (EU MDR 2017/745, MDCG 2020-10/IMEDDEV 2.12/1: GUIDELINES ON A MEDICAL DEVICE VIGILANCE SYSTEM)
serious adverse event if appropriate action had not been taken, intervention had not occurred, circumstances had been less fortunate is considered a reportable event.	Provide all relevant source documentation (de-identified/ pseudonymized) for reported event.	
 Upon request of sponsor
Adverse Event including Adverse Device Effects	Complete AE eCRF page, which contains such information as date of AE, treatment of AE resolution, assessment of seriousness and relationship to the device.	
 In a timely manner but recommend within 10 business days after becoming aware of the information Upon request of sponsor
	Provide all relevant source documentation (de-identified/ pseudonymized) for reported event.	

17.5. *Device Deficiencies*

Device deficiencies will be documented and reported to BSC. If possible, the device(s) under study should be returned to BSC for analysis. The return instructions of the device refer to the return process of the product after market. It shall be returned by the supplier and relevant personnel of the hospital's instrument department. If these device can't be returned, the reason and final disposal will be documented. Device deficiencies and failure to function properly shall also be recorded in the subject's medical record.

Device deficiencies are not adverse events. However, an adverse event that results from a device deficiency, would be recorded as an adverse event on the appropriate eCRF.

17.6. *Reporting to Regulatory Authorities / IRBs / ECs / Investigators*

BSC is responsible for reporting adverse event information to all participating Principal Investigators, IRBs/ECs and regulatory authorities, as applicable.

The Principal Investigator is responsible for informing the IRB/EC, and regulatory authorities of UADEs and SAEs as required by Chinese regulations.

BSC shall notify all participating study centers if SAEs/SADEs or Device Deficiencies occur which imply a possible increase in the anticipated risk of use of the device or if the occurrence of certain SAEs/SADEs demands changes to the protocol or the conduct of the study in order to further minimize the unanticipated risks.

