For data collection retrospectively, BSC shall report all SAEs and device deficiencies that may lead to SAE to the regulatory authorities in Shanghai and Hainan within 10 working days within the events identified or collected, and shall notify ECs in a timely manner during data collecting.

For data collection prospectively, BSC shall report all SAEs and device deficiencies that may lead to SAE to the regulatory authorities in Shanghai and Hainan within 5 working days upon receipt of such information, and shall notify investigators/investigation site and ECs in a timely manner.

18. Informed Consent

Subject participation in this clinical study is voluntary. The Investigator is responsible for ensuring that Informed Consent is obtained prior to study-required procedures and/or testing, or data collection for subjects enrolled prospectively. For subjects enrolled retrospectively, informed consent process of the protocol specified approved by EC will be followed.

The obtaining and documentation of Informed Consent must be in accordance with the principles of the Declaration of Helsinki, ISO 14155, any applicable national regulations, and local Ethics Committee and/or Regulatory authority, as applicable. The ICF must be accepted by BSC or its delegate (e.g. CRO), and approved by the site's IRB/EC, or central IRB, if applicable.

Boston Scientific will provide a study-specific template of the ICF to investigators participating in this study. The ICF template may be modified to meet the requirements of the investigative site's IRB/EC. Any modification requires acceptance from BSC prior to use of the form. The ICF must be in a language understandable to the subject and if needed, BSC will assist the site in obtaining a written consent translation. Translated consent forms must also have IRB/EC approval prior to their use. Privacy language shall be included in the body of the form or as a separate form as applicable.

The process of obtaining Informed Consent shall at a minimum include the following steps, as well as any other steps required by applicable laws, rules, regulations and guidelines:

- be conducted by the Principal Investigator or designee authorized to conduct the process,
- include a description of all aspects of the clinical study that are relevant to the subject's decision to participate throughout the clinical study,
- avoid any coercion of or undue influence of subjects to participate,
- not waive or appear to waive subject's legal rights,

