## **4 GENERAL STATISTICAL METHODS**

### **4.1 Analysis Sets**

The effectiveness set, and safety set include all subjects who have radiotherapy after injection of SpaceOAR hydrogel.

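### AE rates pool visit-based and record-based ascertainment in one safety denominator, and Protocol 17.1 is not reconciled with the retrospective AE provisions, so pooled rates may be understated

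*Protocol*

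**What the plan says.** **Recording rule.** Protocol 17.1 first lists all adverse events as reportable. It then states: "Any reportable event, experienced by the study subject after informed consent, whether prior to, during or after RT, must be recorded in the eCRF". It gives no rule for events before consent.

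**Retrospective provisions.** For subjects who finished radiotherapy (RT) before kick-off, the synopsis and section 6 say that "clinical data will be collected retrospectively, such as data related to radiotherapy, AE (if any) and MRI (if any"). The note closing Protocol 9.4 adds: "The clinical data before participation will be collected retrospectively at same time". Table 17-3 in section 17.4 sets an eCRF timeline for unanticipated device effects, serious AEs and device deficiencies: "For data collected retrospectively, within 5 business day of the event identified or collected during data collection". Its row for other AEs has one timeline for everyone: "In a timely manner but recommend within 10 business days after becoming aware of the information". Section 17.6 adds a sponsor duty: "For data collection retrospectively, BSC shall report all SAEs and device deficiencies that may lead to SAE to the regulatory authorities".

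**Consent and missing data.** Under Protocol 8.1, consent from already irradiated subjects depends on whether prospective follow-up visits can take place. Under Protocol 13, missing retrospective data are not deviations.

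**Analysis.** SAP 4.1 says the "safety set include all subjects who have radiotherapy after injection of SpaceOAR hydrogel", and Protocol 10.2.1 agrees. SAP 5.2.4 defines the AE rate as the percentage of subjects with at least one episode, without a cohort split. SAP 3.2.2, which governs the rectal AE endpoint, has none either.

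**The concern.** The sentence in 17.1 fits a subject who consents before RT. For a subject irradiated before consent, the acute period (which Protocol 4.1 places during RT and the following twelve weeks) may lie partly or wholly before the point at which 17.1 makes recording mandatory. Some such subjects may never have a period after consent.

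The two cohorts are therefore observed differently. Table 9-1 schedules AE assessment before RT, during RT and at four visits afterwards. A retrospective subject's earlier events come from records, with no stated look-back start, source list or completeness rule, and gaps do not appear as deviations. Mild rectal events are plausibly the ones least often written down.

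Rectal AEs and device-related AEs are secondary endpoints, safety is part of the study objective, and SAP 2 foresees use in manuscripts and regulatory submissions. If a subject counts in the denominator while some of his events are missed, the subject-level rate falls, in the direction that favours the device.

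**Working it through.** The documents give no AE rate, safety precision target or retrospective share, so there is no plan figure to reproduce. The check has three parts.

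**1. Passages side by side.** Sections 6, 9.4, 17.4 and 17.6 place AEs from before participation within planned collection. Section 17.1, read alone, sets a recording duty only for later ones. The explicit retrospective timelines cover unanticipated device effects, serious AEs and device deficiencies. The row for other AEs runs from awareness and has no retrospective rule of its own. So 17.1 is unreconciled with the rest, and non-serious events found in records are the least clearly covered.

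**2. Possible effect on a pooled rate.** Let f be the share of the safety set irradiated before consent and c the share of those subjects with an event whose event is captured. Both are assumed. Assume also the same true rate p and the same observation window in both cohorts, and complete capture in the prospective one. Then

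observed rate / true rate = 1 − f × (1 − c)

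| f | c = 0 | c = 0.5 | c = 1 |
|---|---|---|---|
| 0.10 | 0.90 | 0.95 | 1.00 |
| 0.25 | 0.75 | 0.875 | 1.00 |
| 0.50 | 0.50 | 0.75 | 1.00 |
| 0.75 | 0.25 | 0.625 | 1.00 |

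The column c = 0 is an outer bound, since it contradicts the planned retrospective collection. If f = 0 or c = 1 there is no effect.

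For scale, take f = 0.5, c = 0.5 and 20 subjects, with p borrowed from the background in Protocol 4.1 as illustration only:

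- p = 2% (3-year grade 1+ rectal toxicity with the spacer): 2% × 0.75 = 1.5%, a loss of 0.5% × 20 = 0.1 subject.
- p = 9.2% (the same without it): 9.2% × 0.75 = 6.9%, a loss of 2.3% × 20 = 0.46 subject.
- p = 24% (upper late grade 2 or higher figure for IMRT): 24% × 0.75 = 18%, a loss of 6% × 20 = 1.2 subjects.

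**3. Precision if cohorts are shown separately** (exact two-sided 95% intervals, 20 subjects).

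- Zero events: the upper limit is 16.8% for 0/20, 30.8% for 0/10 and about 52% for 0/5 (the prospective cohort if f = 0.75).
- Five events, all among 10 prospective subjects and none found among 10 retrospective: 5/20 = 25% (8.7% to 49.1%) pooled, 5/10 = 50% (18.7% to 81.3%) in the prospective cohort. The pooled figure alone would not show this contrast.

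**The case against.** A reader might infer from 17.1 that AE recording is required only after consent, so that earlier events are never collected. The documents do not say so. The word only is not there, 17.1 opens by making all AEs reportable, and sections 6, 9.4, 17.4 and 17.6 provide for retrospective AEs. That answer stands: the defect is one sentence left unreconciled.

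A reader might also infer that pooled rates are in fact diluted. That needs f above zero and c below one, and neither is documented. The 9.4 note also provides applicable follow-up for AEs after already irradiated subjects join. Protocol 4.1 says late rectal symptoms may take 6 to 12 months or longer to appear, so part of their risk period can be actively observed. Observation windows may differ between cohorts in either direction. SAP 7.3 mentions visit completers as the denominator and is not reconciled with 4.1, so even a full denominator for each retrospective subject is not certain. These points stand.

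Finally, the study is descriptive, the patient pool is small, and SAP 5.2.4 already lists every site-reported AE. This limits the weight of the point but does not remove it. No stated listing content identifies the cohort, and no provision separates the rates.

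**Conclusion.** The inconsistency in 17.1 and the pooling of two ascertainment methods are both confirmed from the text. Understatement of pooled AE and rectal AE rates is plausible and its likely direction is downward, but it is not established. Its size depends on f, c and p, none of which the documents give for this study. Across the range shown, the ratio of observed to true rate runs from 1.00 (no effect) to 0.25 (f = 0.75, with no retrospective capture at all, which the documents do not support).

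It is also tempting to treat the prospective column as the main safety estimate. The documents do not support that either. Both cohorts are enrolled deliberately because the patient pool is limited, and the prospective cohort alone could be as small as 5 of 20 at f = 0.75. Showing both columns beside the total is enough. This is a cheap improvement to reporting, not a flaw that invalidates the safety analysis.

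**What to change.** **SAP.** In 5.2.4, and for the rectal AE endpoint under 3.2.2, tabulate AEs by prospective and retrospective cohort beside the total. Give the number at risk and the observation window for each column, and add a note that retrospective ascertainment is record-based. Do not name either column as the lead estimate. This needs no new data. SAP 5.3 allows it through an amended SAP approved before the primary endpoint analysis. The cost is small cohort denominators and wide intervals with 14 to 20 subjects.

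**Protocol, if it is amended.** Reconcile 17.1 with sections 6, 9.4, 17.4 and 17.6 so that AEs found in records from before consent are recorded, and state the look-back window and sources. Protocol 12 and 14.3 require ethics committee approval. The SAP is dated April 2024, against a protocol of January 2022 with a planned duration of about 15 months, so this edit may come too late to change collection. The SAP change does not depend on it.
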